## **2 PANCREATIC CANCER CHW INTERVENTION**

### **I. PRESURVEY AND INTRODUCE PATIENTS TO DIGITAL APPLICATIONS**

**When?** Within 7 days of diagnosis

**Setting:** in person or by phone. Format: 1 on 1 or in small groups

**Duration:** 1 hr.

**Goal:** Administer surveys before the intervention and introduce patients to the Twillio-SMS and educational videos.

### **II. SESSION 1. Basic information and emotional resources**

**Goal:** To develop trust and address immediate reactions/needs

**When?** During week 2

**Setting:** In-person ideally or over Zoom if preferred by the patient. Involves the patient and their caregiver.

**Duration:** 60-120 minutes

#### **A. MEDICAL INFORMATION**

1. Provide basic information and prognosis about pancreatic cancer – types, stages, procedures and treatment options (surgery, chemotherapy by mouth or IV, radiotherapy, experimental?)
2. Discuss patient and caregiver(s) expectations and possible physical challenges over the next weeks
3. Discuss support at home during and after visits to the clinic or treatments
4. Nutritional advice specific to patients following pancreatic cancer treatment plan
5. Recommended physical activity / physiotherapist according to the patient's Abilities

#### **B. EMOTIONAL AND MENTAL HEALTH:**

1. Tips to address new cancer diagnosis
2. Tips to adapt everyday life to the reality of pancreatic cancer and f/up
3. How to face inability to engage in more physical activity (for those that were used to exercise frequently)
4. Share with patient and caregiver(s) possible emotional and spiritual needs over the next weeks
5. Discuss support at home during and after visits to the clinic or treatments
6. How to talk to Friends and family members about your diagnosis
7. Asking for help
8. Reconnecting strained relationships (family, friends, spiritual)

9. Recognizing and managing anxiety, depression and stress (mindfulness, meditation, relaxation techniques)
10. Tips to developing a positive and resilient approach to life
11. Professional psychological support (individual or family therapy)

### **C. REVIEW OF TWILLIO AND DOCOLA APPS USE**

#### **D. Palliative care and other resources**

- Connecting with palliative team
- Caregiver selection
- Intro to Support groups
  - LLUC support groups for caregivers meet on Sundays (English only)
  - California Caregiver Resource Center online and in person.
  - Identifying meaningful new skills, hobbies, social activities

### **III. SESSION 2. Practical resources and addressing new questions**

**Goal:** win trust and address immediate reactions/needs

**When?** During week 3 (*or week 4 if intervention is 3 months long*)

**Setting:** In-person ideally or over Zoom if preferred by the patient. Involves the patient and their caregiver.

**Duration:** 60-120 minutes

#### **A. MEDICATIONS AND SIDE EFFECTS**

1. Information and management of side effects.
2. Meds and tips information based on patient needs
3. Importance of adhering to treatment?

#### **B. LEGAL DOCUMENTS**

1. Patient rights and legal help
2. Other available resources and services
3. Advance Directives and other legal documents: health insurance and coverage, how to appeal or submit applications, how to request supplies, tools and durable mobile equipment

#### **C. Palliative care (continued)**

#### **D. PRACTICAL SKILLS/WORKSHOPS**

1. Tips to reduce the time burden (too many MDs?/appts?) with MyChart or other tools
  2. Complementary therapies: massage, aromatherapy, music, art therapy, etc....
  3. Cooking classes and recipes.
  4. Physical activities: yoga, Tai chi or other easy exercises
- 

**IV. TELEHEALTH VISIT** with resource person of choice (facilitated by CHWs).

**Goal:** provide customized resources based on patients' needs

**When?** During week 3-6

**Setting:** In groups (online or in-person?) patients and caregiver(s)

**Duration:** 1 hr

(Optional) According to patients' desires or interests, information can be provided about end of life plans (community resources, estate planning, finances, funeral homes, funeral services, etc..)

---

**V. FOLLOW-UP PERIOD** – patients and caregivers (*if program lasts 3 months*)

**Goal:** CHWs weekly calls providing help to problem solve & provide support and if needed can meet the patient in person.

[figure not shown]
**When?** During weeks 7 to 12

**Setting:** Telephone and if needed virtual or in-person.

**Duration:** varie

## Diagram of pancreatic cancer patients' intervention

### Use of Digital Applications

Patients will be provided access to web-based educational modules through Docola and Youtube that provide general information about pancreatic cancer, palliative care, and treatment options.

In between the study visits, the patients will receive the Edmonton Symptom Assessment Scale via Twillio-RedCap SMS once a week (an integrated short message system platform in Loma Linda's implementation of RedCap). A positive ESAS is defined as three symptoms with  $> 7/10$  scores. If the CHW receives a positive ESAS, they will call the patient to ask how they are doing and then forward the responses to the Palliative care team, which will triage the patient as needed clinically to respond to these symptoms. The CHW will also ask the patient if they have questions or concerns twice a week using Twillio-RedCap SMS messages.

#### f. **Alternative procedures.**

There are no alternative procedures.

## 8. **INCLUSION / EXCLUSION CRITERIA**

### **Inclusion criteria:**

- Age 18 to 90
- English or Spanish-Speaking
- Diagnosed with Newly-Diagnosed Pancreatic Adenocarcinoma or has a pancreatic mass on CT/MRI with suspected PDAC and is awaiting biopsy.
- Able to communicate verbally to allow for audio recording to complete an exit-interview
- Must be able to consent

**Exclusion criteria:**

- Biopsy Does not Confirm Adenocarcinoma of the Pancreas

**9. RECRUITMENT AND RETENTION**

[name] and the clinical research coordinator (who will be hired and then added to the IRB prior to starting the study) will recruit patients with suspected or newly diagnosed pancreatic cancer from the gastroenterology, oncology and surgical oncology clinics and endoscopy unit (the researcher's patients) No patients outside of the researcher's clinical practice will be contacted regarding the study unless they contact the study investigators first when responding to the study flyer. Pancreatic cancer is diagnosed by endoscopic ultrasound, and patients have a pre-procedure and post-procedure visit where the diagnosis is given and discussed with the patient, and referral to oncology, etc., are made. This is the setting where patients will be included.

Recruitment Method: Study investigators will recruit patients from the endoscopy unit or clinic after a patient is referred with suspected pancreatic cancer or confirmed pancreatic cancer. This method involves recruiting the researcher's own patients.

We will also distribute IRB-approved letters to community oncologists along with an IRB-approved flyer that can be provided to patients which contains a phone number and email that the patient can use to contact the study team. If a patient contacts us expressing interest, then we will recruit them over the phone and then enroll them in the study after obtaining consent.

**10. INFORMED CONSENT PROCESS**

Prior to conducting any study-related activities, written informed consent or electronic informed consent using the MyChart platform will be obtained from the patient either in the clinic, endoscopy unit or prior to the first study visit. The patient will be provided with a signed and dated copy of the informed consent form.

[name], [name], [name] or the clinical research coordinator (who will be hired and then added to the IRB before starting the study) will be responsible for obtaining consent. First the study will be explained to the patient along with its risks and benefits when the patient is first contacted in the clinic or endoscopy unit. After the patient has had any questions answered, if they agree to participate, consent will be obtained in the clinic or endoscopy unit or in the conference room prior to an in-person interview or small focus group.

Authorization for HIPAA will also be obtained as part of the intervention is communicating with the patients medical team and study data may be shared with the Sponsor (DOD/CDMRP).

**11. SCREENING**

Screening procedures will be performed in the seven days prior to enrollment for the researcher's own patients and occur as the investigator reviews the patient's chart to perform a clinical visit to inform or obtain the diagnosis of pancreatic

adenocarcinoma. We will not screen any patients not under the care of the study investigators.

If any patients outside of our care are interested in the study and contact us via phone or email, we will only screen them for the study after they are consented with HIPAA authorization obtained and if they meet the inclusion criteria, at that point they will be enrolled.

## **12. POTENTIAL RISKS**

- Anxiety or stress related to talking about pancreatic adenocarcinoma.
- Loss of confidentiality.

To mitigate the risk of anxiety and stress, we will let patients guide the conversation with the CHWs so that they can redirect the conversation and what resources they want based on their anxiety/stress level or if some topic is difficult for them to talk about. We also will have their palliative care provider engage with them if they experience any anxiety or stress.

To mitigate the loss of confidentiality, we will de-identify all study documents except the informed consent document (which will be stored either electronically in LLEAP or in a secure locked drawer in the office of [name]). We will use a unique patient ID number on all other study documents. All protected health information collected will be securely stored in an encrypted LLU computer and will not be shared with anyone electronically. Any paper records will be stored in the same locked drawer in [name] office at LLU.

## **13. POTENTIAL BENEFIT(S)**

Patients assigned to the CHW intervention may benefit from it as community health workers are providing care navigation and connecting patients to resources that they may need.

## **14. SUBJECT WITHDRAWAL OR TERMINATION**

*At any time before or after the interview or focus group, a patient may withdraw participation, and their transcribed and recorded interview will be destroyed.*

## **15. COMPENSATION**

We will provide \$10 Amazon gift cards to compensate patients for their time in participating in each study visit. They will receive this gift card regardless of how much of the interview/focus group they complete.

## **16. CONFIDENTIALITY AND PRIVACY**

The primary way we will maintain confidentiality and privacy is by not including any identifying information on any study documents except for the informed consent document (which will be stored either electronically in LLEAP or in a secure locked drawer in the office of [name]). We will use a unique patient ID number on

all other study documents. All protected health information collected will be securely stored in an encrypted LLU computer and will not be shared with anyone electronically. Any paper records will be stored in the same locked drawer in [name] office at LLU. All research data will be on a secure, encrypted LLU computer and will not be transmitted or shared with anyone else.

## **17. DATA COLLECTION AND MANAGEMENT RESPONSIBILITIES**

### **Data Collection**

We will collect baseline demographics data (age, gender, race/ethnicity, date of diagnosis, stage of diagnosis, and treatments) from the patient's chart. We will also administer the following surveys before the first study visit, at 4 weeks and 3 months.

- FACT-HEP (measures HRQoL) - 30 questions
- NCCN-FACT Hepatobiliary-Pancreatic Symptom Index – 18 questions
- Palliative Care Attitude Survey (PCAS-9) – 9 questions
- ACP (Advanced care planning engagement) survey – 4 questions
- Acceptability of intervention measure (AIM) survey – 4 questions
- Technology Comfort (our survey) – 12 questions

### **Storage**

At the time of patient enrollment each patient will be given a unique identification number. The key that correlates the unique identification number will be stored on a secure encrypted computer at Loma Linda. Apart from the informed consent, all other documents will not have any patient information written on them. They will only have the unique identification number.

RedCap will be used to store all the study data for this study. As described above this data is deidentified and the RedCap ID serves as the unique identification number. After the patient fills out the paper version of the questionnaire the data will be entered in RedCap by a study investigator and then those paper form which do not contain any identifiable information will be shredded.

Then after the data collection is completely entirely for all patients and the study is completed, we will destroy the electronic copy correlating names to keys which was stored on a secure computer at Loma Linda. At this point all the study data will be deidentified and stored in RedCap. When the study analysis is completed then all the data will be deleted from the computer.

### **Record Retention**

Records of data generated in the course of this study will be de-identified and will be kept for at least 6 years and then destroyed. Prior to destruction, data can be used for other IRB approved research.

## **18. STATISTICAL ANALYSIS**

**Quantitative Analysis.** We will first determine the distribution of the primary and secondary outcomes for the usual care and CHW arms by using a Shapiro–Wilk test to assess the normality for these outcomes. Then accordingly we will report either a mean (standard deviation) or a median (95% confidence interval) for both arms for the NCCN-FACT Hepatobiliary-Pancreatic Symptom Index and FACT-Hep scores and then use the standard deviation or variance for the power analyses for a larger definitive subsequent RCT. We will also use a t-test and Wilcoxon rank-sum test to compare the differences between these measures between the two groups at different time points. To assess a preliminary pre/post effect, we will compare survey data between baseline and 4 weeks using generalized linear models to compute contrasts for continuous variables from the FACT-Hep subscores, NCCN-FCAT HPBSI, PCAS-9, and ACP Engagement Survey scores.

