---

1. **PROTOCOL INFORMATION**

Study Title: To evaluate the preliminary efficacy of our digitally enhanced CHW-led intervention in newly diagnosed PDAC with a pilot randomized controlled trial of 60 PDAC patients comparing the intervention to attention control with usual care

Date: 9/1/2025

Funding Source: DOD/CDRMP

Phase of Study: N/A

Version Date of Protocol: 1.0

3

2. **PRINCIPAL INVESTIGATOR'S INFORMATION**

PI Name, Title: [name], Assistant Professor

Name & Address of Research Institution: Loma Linda University Division of Gastroenterology and Hepatology, [name]

[contact]

Fax #:

Email Address: [[contact]](mailto:[contact])

3. **STUDY PERSONNEL INFORMATION**

Study Staff Name, Title: [name]

[contact]

[contact]

Email Address: [[contact]](mailto:[contact])

Study Staff Name, Title: [name] [name]

[contact]

[contact]

Email Address: [[contact]](mailto:[contact])

4. **STUDY INFORMATION**

Location(s) of Research Activity: Loma Linda University Medical Center

Expected Start/Stop Dates of Research: 07/1/2025 to 07/01/2027

Special Time Sensitivities: Funded through a 2-year grant from the DOD.

Type of Research: Prospective

Anticipated Enrollment number: 60

Patient Population: Patients with pancreatic ductal adenocarcinoma

5. **PURPOSE**

The purpose of this study is to obtain a preliminary estimate of the impact of a community health worker-led intervention by understanding the variance of the primary outcomes (symptom burden and quality of life) using a pilot randomized controlled trial.

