## 6. **OBJECTIVES AND PURPOSE**

**Objective:** To evaluate the preliminary efficacy and the variance of primary outcomes (symptom burden and quality of life) of our digitally enhanced CHW-led intervention in newly diagnosed PDAC with a pilot randomized controlled trial of 60 PDAC patients comparing the intervention to attention control with usual care.

- 1 Hypothesis H1: Compared to attention control with usual care the digitally enhanced CHW-led intervention is expected to decrease NCCN-FACT Hepatobiliary-Pancreatic Symptom Index scores and improve HRQoL compared to baseline.

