**c. Endpoints**

The primary endpoint will be change in the symptom burden, measured by the NCCN-FACT Hepatobiliary-Pancreatic Symptom Index and quality of life, measured by the FACT-HEP instrument.

Secondary endpoints include the change in the PCAS-9, ACP Engagement Survey, and ACP completion rates. Other secondary outcomes include direct healthcare costs, ER/urgent care utilization, and response/usage rates to the SMS questions.

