**d. Overall study design**

This will be a pilot randomized controlled trial where we will plan on randomizing patients with PDAC in a 1:1 fashion to receive a digitally-enhanced community health worker intervention that will involve visits with the CHW and digital communication to facilitate care navigation and provide early palliative care engagement or usual care with attention control.

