### **Study Intervention**

Usual Care consists as follows:

An attention control where patients are provided handouts from PANCAN and videos from the NPF and study staff contact them monthly over video to administer the surveys for the outcomes but also answer any questions.

After a PDAC diagnosis is made, referrals are made to Medical and Surgical Oncology and Palliative Care, and the patient follows up in the Gastroenterology clinic to discuss the diagnosis and related symptoms. Baseline surveys will be completed at the time of enrollment in both the usual care and CHW-led intervention arms.

The CHW-led intervention arm will receive the same care/referrals as usual care but in addition work with a CHW as follows:

The study visits will take place in person in the clinic, School of Behavioral Health conference room, or the patient's home or virtually using Microsoft Zoom (depending on the patient's preference).

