### **Randomization**

The intervention each patient will receive will be randomized using a uniform random number generator (<https://www.randomize.net/>) with stratification by either metastatic PDAC or resectable/borderline resectable PDAC.

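### Section 18 compares the arms with an unadjusted t-test and Wilcoxon test, leaves unclear whether raw scores or changes are tested, and uses neither the baseline score as a covariate nor the stage stratum

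*Protocol*

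**What the plan says.** All references are to the Protocol.

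- **Endpoint (section 7.c).** "The primary endpoint will be change in the symptom burden, measured by the NCCN-FACT Hepatobiliary-Pancreatic Symptom Index and quality of life", the latter measured by FACT-HEP. The hypothesis in section 6 is also framed against the starting value: the intervention is expected to "improve HRQoL compared to baseline".
- **Baseline data (section 7.e, Study Intervention).** "Baseline surveys will be completed at the time of enrollment in both the usual care and CHW-led intervention arms". Section 17 repeats the surveys at 4 weeks and 3 months.
- **Randomisation (section 7.e).** Allocation is made "with stratification by either metastatic PDAC or resectable/borderline resectable PDAC".
- **Between-arm analysis (section 18).** After a Shapiro–Wilk check and a summary of each arm, the plan is to "use a t-test and Wilcoxon rank-sum test to compare the differences between these measures between the two groups at different time points". No covariate is named.
- **Only model named (section 18).** Generalized linear models are used for a pre/post contrast from baseline to 4 weeks. The text states no arm contrast, covariate or stratum for these models, and they do not cover 3 months.
- **Use of the results (section 18).** The SD or variance of the two primary scores is to feed the power calculation of a later definitive trial.

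**The concern.** The words that define the tests can be taken in two ways. They may compare the scores themselves between arms at each visit, or they may compare changes over time between arms. The measures last mentioned before that sentence are the symptom index and FACT-Hep scores, so raw scores at each visit are the plainer reading. On that reading the tests do not estimate the declared endpoint of change.

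On either reading the comparison makes less use of the data than it could. A baseline value of the same instrument usually predicts the follow-up value, and the stratum was thought important enough to govern allocation. In a trial of 60, a chance difference between arms at baseline also matters. It carries over in part to a raw-score comparison, and in part, with opposite sign, to a change-score comparison.

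The stake is larger for the handover than for any p-value. The pilot exists to supply variance estimates. If only the raw SD is reported, the planners of the definitive trial will have neither the correlation nor the residual SD that an adjusted analysis needs.

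**Working it through.** **Inputs from the Protocol.** "Anticipated Enrollment number: 60" (section 4) and "randomizing patients with PDAC in a 1:1 fashion" (section 7.d) give 30 per arm. The protocol states no SD, correlation, effect size, alpha, power or dropout, so it has no figure of its own to reproduce.

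**Assumptions.** All 30 per arm are analysed, with no dropout. The SD is the same at baseline and follow-up and is set to 1. The correlation r between baseline and follow-up runs from 0.3 to 0.8.

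**Step 1: variance of the arm difference, relative to raw follow-up scores.**

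- Raw follow-up scores: 1
- Change scores: 2(1 − r)
- ANCOVA on baseline: 1 − r²

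The saving from ANCOVA is r² against raw scores. Against change scores it is 1 − (1 − r²)/[2(1 − r)] = (1 − r)/2.

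| r | Change scores | ANCOVA | Saving vs raw scores | Saving vs change scores |
|---|---|---|---|---|
| 0.3 | 1.40 | 0.91 | 9% | 35% |
| 0.5 | 1.00 | 0.75 | 25% | 25% |
| 0.7 | 0.60 | 0.51 | 49% | 15% |
| 0.8 | 0.40 | 0.36 | 64% | 10% |

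**Step 2: standard error.** Unadjusted on raw scores, SE = √(2/30) = 0.258 SD. ANCOVA multiplies this by √(1 − r²):

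- r = 0.5: 0.258 × 0.866 = 0.224 SD, which is 13% lower.
- r = 0.7: 0.258 × 0.714 = 0.184 SD, which is 29% lower.

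**Step 3: small-sample cost of estimating the slope.** The factor is 1 + 1/(2n − 4) = 1 + 1/56 = 1.018 with n = 30.

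- At r = 0.5 the saving against raw scores becomes 1 − 0.75 × 1.018 = 24%.
- At r = 0.7 it becomes 1 − 0.51 × 1.018 = 48%.
- The half-width of the 95% CI goes from 0.52 SD to 0.45 SD (r = 0.5) or 0.37 SD (r = 0.7).
- Break-even against raw scores is at r² = 1/57, so r is about 0.13. Below that, adjustment costs under 2% of variance.

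**Step 4: the stratum.** It contributes nothing to the figures above, which come from the baseline score alone. Its effect was checked separately by simulation: 20,000 trials, two equal strata, exact balance of arms within strata, nominal two-sided 0.05. The unadjusted t-test rejected a true null in 4.3%, 4.0% and 2.7% of trials when stage explained 5%, 10% and 20% of the outcome variance. These shares and the exact balance are assumptions. Ignoring the stratum therefore tends to make the test conservative.

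**Step 5: handover to the definitive trial.** If that trial is analysed by ANCOVA but sized from the raw SD, its sample size is too large by a factor of 1/(1 − r²): 1/0.91 = 1.10 at r = 0.3, 1/0.75 = 1.33 at r = 0.5 and 1/0.51 = 1.96 at r = 0.7. If it is analysed on change scores, the raw variance is wrong by the factor 2(1 − r): too small at r = 0.3 (1.40) and too large at r = 0.7 (0.60).

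**The case against.** Five points can be made for the plan.

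1. **The tests may be on changes.** The phrase can mean differences over time, compared between arms. That would agree with section 7.c and with the hypothesis. This stands as a possible reading. Baseline would then enter the comparison, and the conflict with the endpoint would disappear. ANCOVA would still save 15% to 25% of variance for r from 0.7 to 0.5, and the stratum would still be left out.
2. **Baseline is used elsewhere.** The generalized linear models do use it. A reader might infer that section 18 ignores baseline altogether, and that is not so. But the models serve a pre/post contrast to 4 weeks with no stated arm contrast, so they do not fill the gap.
3. **The loss is not established.** A reader might infer that the plan throws away a quarter to a half of its precision. The document does not support that as a fact. The figure is r² for an assumed r of 0.5 to 0.7, holds only on the raw-score reading, and refers to variance. The standard error falls by 13% to 29%.
4. **There may be one test per comparison.** A reader might count eight p-values (2 outcomes × 2 follow-ups × 2 tests). Since a Shapiro–Wilk check comes first, the intent may be to choose one test according to its result, which gives four. The text does not settle it.
5. **This is a pilot, and an SAP may add covariates.** No power is claimed, the unadjusted tests are valid, and the correlation could be computed later from the same data. That limits the weight of the point. It does not remove it, because the protocol itself names the between-arm tests and names the SD as the planning input.

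**Conclusion.** The point holds as a shortfall in efficiency and clarity. Section 18 fixes an unadjusted between-arm comparison, does not say whether it is of scores or changes, and makes no use of the stratum. The available gain depends on a correlation that the protocol does not give. With 30 per arm analysed, no dropout and equal SDs, the variance saving for r from 0.3 to 0.8 is 9% rising to 64% against raw scores, and 35% falling to 10% against change scores. ANCOVA is the better choice on both readings over that whole range.

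A reader might go further and infer that the planned tests are biased or invalid. They are not: randomisation keeps the comparison unbiased, and leaving out the stratum tends to make the test conservative. The most lasting consequence is that a raw SD on its own is not enough to plan an adjusted definitive trial.

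**What to change.** In section 18:

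- State that, for each primary outcome at 4 weeks and at 3 months, the arm difference is estimated by ANCOVA of the follow-up score on arm, baseline score and randomisation stratum, or by the equivalent visit contrast of a mixed model. Report it with a 95% CI. With baseline as a covariate, the arm difference in follow-up score equals the adjusted arm difference in change, so this also matches section 7.c.
- Keep one rank-based analysis, labelled as a sensitivity check, in place of the undetermined pairing of two tests.
- Report the residual SD and the baseline-to-follow-up correlation for each outcome alongside the raw SD, as inputs to the definitive trial's sample size.

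The cost is a few sentences. The baseline scores and the stratum are already collected, so no new data, visits or patients are needed.

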PDAC patients have low health-related QoL (HRQoL), around the initiation of treatment. For patients receiving palliative chemotherapy, baseline QoL was significantly impaired, and 39% had deterioration in QoL by 3 months and 59% by 6 months. We conducted a prospective cohort study that followed 111 patients with newly diagnosed PDAC. We demonstrated that 72% of patients had a clinically significant decrease in the physical and mental well-being domains of HRQoL at 30 days. In particular, Hispanics with PDAC were found to have significantly lower physical and mental HRQoL than other ethnic groups.

Early initiation of palliative care has been shown to improve HRQoL and overall survival in patients with different solid tumors. Palliative care also increases advanced care planning (ACP) and reduces overall healthcare costs. Regarding PDAC, SEER-based

analyses demonstrated that most palliative care encounters for PDAC occurred near the end of life and were not associated with lower costs. Nevertheless, palliative care encounters within 30 days of diagnosis reduced the number of ED visits, rate of ICU admission, and overall healthcare costs. Multiple clinical trials have demonstrated that early palliative care within 2-4 weeks of diagnosis can improve physical, social, emotional, and functional HRQoL. However, Hispanic PDAC patients are less likely to receive palliative care or hospice referrals than non-Hispanic Whites. Despite evidence that palliative care initiation may benefit PDAC patients, there is limited data on the impact of initiating palliative care at the time of diagnosis in this population.

PDAC patients report critical misconceptions about the treatment of PDAC. They overestimated the effectiveness of aggressive treatments, including surgery. Furthermore, 50% of patients believed that undergoing every possible treatment was the only approach to their disease. Patients with metastatic PDAC expressed that the goal of treatment was improving their survival, and were unsure that palliative care could address symptoms and improve their quality of life. These studies illustrate significant patient misconceptions regarding treatment options, the goal of treatment, and the availability of palliative care.

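### The only model-based analysis in section 18 is a baseline-to-4-week contrast with no arm comparison; a baseline-adjusted between-arm contrast at both follow-up visits would serve the aim better and needs no new data

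*Protocol*

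**What the plan says.** The trial is randomised: "we will plan on randomizing patients with PDAC in a 1:1 fashion", with 60 patients in total. The objective is preliminary efficacy against attention control with usual care, together with the variance of the primary outcomes. Section 7.c sets the endpoint as change: "The primary endpoint will be change in the symptom burden, measured by the NCCN-FACT Hepatobiliary-Pancreatic Symptom Index and quality of life". It names no time point. Section 17 gives the schedule: "We will also administer the following surveys before the first study visit, at 4 weeks and 3 months".

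Section 18 plans two inferential analyses.

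- Between the groups, a t-test and a Wilcoxon rank-sum test of the measures just named, which are the NCCN-FACT index and the FACT-Hep scores. The time points are left open, and the sentence does not say whether scores or changes from baseline are compared.
- A model: "To assess a preliminary pre/post effect, we will compare survey data between baseline and 4 weeks using generalized linear models to compute contrasts". It covers the FACT-Hep subscores, the NCCN-FACT index, PCAS-9 and the ACP Engagement Survey. No arm comparison is named, and neither the 3-month survey nor the randomisation stratum appears.

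H1 in section 6 carries two comparators. It opens "Compared to attention control with usual care the digitally enhanced CHW-led intervention is expected to decrease NCCN-FACT Hepatobiliary-Pancreatic Symptom Index scores", and the same sentence ends with a comparison to baseline.

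**The concern.** A baseline-to-4-week contrast, taken within one arm or pooled over both, measures everything that happens to patients over those weeks: disease course, cancer treatment, usual supportive care and any CHW effect. Only a comparison with the control arm isolates the last of these.

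The protocol itself gives reason to expect movement without the intervention. Section 7.a reports that "72% of patients had a clinically significant decrease in the physical and mental well-being domains of HRQoL at 30 days", over almost the same interval. If the intervention slows decline, a pre/post contrast can show no benefit or apparent harm. If scores improve in both arms, it credits that improvement to the CHW. Both arms receive palliative care referral, and controls also get educational material, so PCAS-9 and ACP scores could move in either arm.

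The exposure is greatest for PCAS-9 and ACP Engagement. On the natural reading of section 18, the between-group tests cover only the two primary scores, so these two secondary scores would have only the uncontrolled contrast. At stake is the preliminary efficacy estimate that would inform a definitive trial.

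**Working it through.** The protocol gives no alpha, power, effect size, SD or correlation, so there is no figure of its own to reproduce.

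**Inputs from the protocol:** 60 patients, 1:1, so 60/2 = 30 per arm; surveys at baseline, 4 weeks and 3 months.

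**Assumptions:** two-sided alpha 0.05; SD 1 at each visit; baseline-to-4-week correlation rho of 0.3, 0.5 or 0.7; common drift in both arms of 0, -0.3 or -0.5 SD.

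**1. What the pre/post contrast estimates.** Expected change in the CHW arm = benefit - decline. With an assumed benefit of 0.3 SD and a decline of 0.5 SD, this is 0.3 - 0.5 = -0.2 SD. For a decline of 0.3 to 0.7 SD it runs from 0.3 - 0.3 = 0.0 to 0.3 - 0.7 = -0.4 SD. The between-arm difference in change is 0.3 SD throughout.

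**2. Rejection rates with no treatment effect** (20,000 simulated trials per setting; bivariate normal scores):

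| rho | Common drift (SD) | CHW arm pre/post, paired t | Between-arm t on change |
|---|---|---|---|
| 0.3 | 0 | 5.0% | 4.8% |
| 0.3 | -0.3 | 27.1% | 5.2% |
| 0.3 | -0.5 | 60.9% | 5.1% |
| 0.5 | 0 | 5.0% | 4.9% |
| 0.5 | -0.3 | 35.6% | 5.0% |
| 0.5 | -0.5 | 76.2% | 4.9% |
| 0.7 | 0 | 5.2% | 5.1% |
| 0.7 | -0.3 | 53.5% | 5.0% |
| 0.7 | -0.5 | 92.7% | 5.2% |

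With negative drift the significant results are essentially worsening, which here has nothing to do with the intervention. The between-arm test is unaffected by common drift.

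**3. What baseline adjustment gains.** Detectable difference at 80% power = (1.960 + 0.842) x sqrt((2/30) x v), in SD units. Here v = 1 for the 4-week score alone, 2(1 - rho) for change, and 1 - rho^2 for the baseline-adjusted score. With v = 1 this is 2.802 x 0.2582 = 0.72.

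| rho | 4-week score alone | Change | Baseline-adjusted |
|---|---|---|---|
| 0.3 | 0.72 | 0.86 | 0.69 |
| 0.5 | 0.72 | 0.72 | 0.63 |
| 0.7 | 0.72 | 0.56 | 0.52 |

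Whether the planned t-test uses scores or change therefore matters, and the baseline-adjusted analysis has the smallest detectable difference at each rho.

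**4. Conditional check on pairing.** If the model treated a patient's two scores as independent, the pre/post standard error would be too large by sqrt(2)/sqrt(2(1 - rho)) = 1/sqrt(1 - rho): 1.20, 1.41 and 1.83 at rho 0.3, 0.5 and 0.7. With no drift, the actual size of a nominal 5% test would fall to 1.9%, 0.6% and 0.03%. That error is conservative.

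**The case against.** The strongest reply is that the randomised comparison is already planned. The sentence just before the model sets out between-group tests of both primary scores, and such tests hold about 5% error under any common drift. The model is labelled preliminary and pre/post, and the pilot's purpose includes estimating variance. This stands, and it limits the point. A reader might infer that the plan discards the control arm or never tests H1 between arms; section 18 does not support that.

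Other stronger readings also fail.

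- **Within-patient correlation is ignored.** This would be inferred from silence. The text names no covariance structure and excludes none, and an analysis plan not shown may supply it. Nor does the text say whether the contrasts are within arm, pooled or by arm.
- **The FACT-Hep total goes unanalysed.** FACT-Hep scores are summarised by arm and compared between groups; only the model is confined to subscores.
- **H1 is a pre/post hypothesis.** Its closing words, "is expected to decrease NCCN-FACT Hepatobiliary-Pancreatic Symptom Index scores and improve HRQoL compared to baseline", can be read with its opening as a between-arm difference in change.
- **The 72% fixes the size of the drift.** It is a proportion of patients, not a mean shift, and section 7.a does not tie it to either primary instrument. It says nothing about PCAS-9 or ACP scores.

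What the reply does not answer is that the one model named specifies no arm comparison and leaves out the 3-month survey, while the between-group tests are unadjusted and do not settle score against change for an endpoint defined as change.

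**Conclusion.** The point holds as a free improvement to the analysis, not as a failure to make the randomised comparison. Followed as written, the pre/post contrast cannot support an efficacy estimate against control. On the natural reading it is the only analysis comparing PCAS-9 and ACP Engagement scores, although the opening of section 18 mentions secondary outcomes and a wider reading of the between-group tests is possible.

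The size depends on assumptions. The rejection rate of 61% to 93% needs a common 0.5 SD decline; at 0.3 SD it is 27% to 54%, and with no drift it is the nominal 5%. The gain from baseline adjustment over the 4-week score alone is small at rho 0.3 (0.72 to 0.69 SD) and useful at 0.5 and 0.7 (0.63 and 0.52 SD). The qualitative conclusion needs none of these values: a contrast without a control arm cannot separate treatment from disease course.

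**What to change.** In section 18, replace the pre/post contrast with a between-arm contrast for each primary score and each continuous secondary score, at 4 weeks and at 3 months. Adjust for the baseline score and the stage stratum used in randomisation. ANCOVA at each visit is sufficient; a repeated-measures model that accounts for within-patient correlation is an equally acceptable choice. Report each contrast with its 95% CI, and use the FACT-Hep total for the primary quality-of-life outcome. If the t-test and Wilcoxon tests are kept as supporting analyses, state the visit and whether they compare scores or change.

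Keep within-arm change and FACT-Hep subscores as descriptive. Word H1, where it appears in sections 6 and 7.b, as the between-arm difference in change from baseline.

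The cost is text in section 18 and H1. Baseline scores, the stratum and the 3-month surveys are already collected, so no new data, visits or patients are needed.
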